8.3.4. Interim Analysis

No interim analysis is planned for this study.

8.3.5. Key Elements of Analysis Plan

8.3.5.1. Efficacy Analyses

The primary analyses of the primary and secondary efficacy endpoints are described in Section 8.3.3. The details of any further planned analyses, including subgroup analysis and exploratory endpoints, will be provided in the RAP.

8.3.5.1.1. *Impact of Missing Data on Primary Endpoint*

Missing data are not explicitly imputed in the primary MMRM analysis; although, there is an underlying assumption that data are missing at random, including those withdrawn for lack of efficacy. All available scheduled postbaseline assessments up to endpoint are utilized and, via modelling of the within subject correlation structure, the derived treatment difference at Week 26 is adjusted to take into account missing data. The MMRM analysis (using saturated fixed effects and an unstructured variance-covariance matrix) is considered appropriate as the primary method of analysis, as it has been shown to give sensible answers to on-treatment questions in a range of practical situations [Siddiqui, 2009].

8.3.5.1.2. *Extent of Missing Primary Analysis Data*

Missing data is expected to arise mainly from subjects missing complete visits. The amount of missing data for those baseline covariates included in the statistical analysis is expected to be none or at worst minimal. If it should occur, that subject will effectively be lost to analysis. Missing data for HbA_{1c} between two nonmissing visits will be considered missing at random (intermediate missing data).

In this study, subjects who withdraw from treatment will be withdrawn from the study. In the eCRF, the reason for treatment discontinuation and the reason for withdrawal from the study are collected separately. Whenever the HbA_{1c} value at Week 26 is missing (end of the study), the reason can be determined based on available data in these two locations. The reason for missing data can be classified as follows: safety, procedural (including withdrawal of consent), or lack of efficacy.

8.3.5.1.3. *Reasons for Withdrawal*

Reasons for withdrawal are assumed to fall into three broad categories:

- Procedural (e.g., lost to follow-up, withdrew consent, protocol deviation, study closed/terminated, and investigator discretion): In this case, it is expected that an assumption of missing at random (MAR) is appropriate for imputation of HbA_{1c} data after withdrawal.

- Safety (e.g., AE, subject reached protocol-defined stopping criteria): It is expected that, in most cases, any change in safety related to these reasons for withdrawal would have been captured prior to the subject withdrawing from the study. In Study GLP108486 (albiglutide versus lispro over background glargine), 5% of subjects in the albiglutide group and <1% in the lispro group had AEs leading to withdrawal of active treatment through Week 26. In the albiglutide group, the most common AE leading to withdrawal was injection site reaction (1.1%). Missing HbA_{1c} values after withdrawal due to safety concerns will be considered to possibly be missing not at random (MNAR).
- Lack of efficacy: In this treat-to-target study, a substantial number of cases of withdrawal due to lack of efficacy is not expected. Missing HbA_{1c} values after withdrawal due to lack of efficacy are considered to possibly be MNAR.

Sensitivity analyses will be performed for data missing due to safety concerns or due to lack of efficacy.

8.3.5.1.4. Handling of Missing Data

The impact of missing data will be explored, as outlined below, for the Full Analysis Population only.

Examination of Missing Data Patterns

To examine the nature of missing data, cohorts of subjects will be defined based on the scheduled assessments (HbA_{1c} change from Baseline) that were completed at Weeks 4, 5, 10, 18, 26.

1. Subjects who have week 4 assessment only
2. Subjects who have assessments up to and including Week 5 only
3. Subjects who have assessments up to and including Week 10 only
4. Subjects who have assessments up to and including Week 18 only
5. Subjects who have assessments up to and including Week 26.

The number and percentage of subjects on each treatment in the 5 cohorts defined here will be tabulated. Graphical methods will be used to examine changes from Baseline over time to assess the pattern of outcomes prior to withdrawal.

Sensitivity Analyses – Multiple Imputation

Sensitivity analyses using multiple imputation methods will be conducted. Firstly, missing data between two nonmissing time points will be considered missing at random.

The following multiple imputation methods are proposed based on whether data are missing at random or not at random:

1. All missing data assumed MAR: Imputation is based on means and variances-covariances from subjects in the same treatment group as the withdrawn

subject and is comparable to MMRM. The main differences are that this approach uses separate covariance parameter estimation for each arm, and also separate regression parameters are estimated on baseline covariates within each arm. This more complex parameterization of the imputation model compared with the analysis model is valid. This approach will be used for all data missing post withdrawal. Here the estimand is one where after withdrawal all subjects progress in a similar way to those who remain in the trial. We expect the MMRM and this to give similar answers. If so, then it indicates any difference between the primary MMRM analysis and multiple imputation sensitivity analysis is due to the assumed effect modification and the assumed rates of HbA_{1c} increase after withdrawal, rather than anything to do with going from an MMRM approach to a multiple imputation approach.

2. Missing due to lack of efficacy or due to safety concerns using last mean carried forward (LMCF), that is MNAR: This approach assumes that a constant rate of increase in HbA_{1c} change from Baseline is experienced by subjects following withdrawal from the study for lack of efficacy or due to safety concerns. The MAR approach will be used for missing data due to procedural reasons. Sensitivity analyses using the LMCF approach will be performed using the following rates of HbA_{1c} increase: 0%/month, 0.1%/month, and 0.2%/month to explore the potential impact as in a tipping-point analysis. For each treatment group, these 3 rates will be assumed, resulting in 9 scenarios. The resulting treatment differences and associated P-values for noninferiority will be tabulated against the varying rates of HbA_{1c} increase. This estimand is one where those who withdraw for lack of efficacy or for safety concerns are assumed to revert to an unstable treatment regimen with an increasing rate of HbA_{1c}.

For each imputation data set, an analysis of variance will be carried using Week 26 data, both actual and imputed, using the same covariates as in the primary analysis. Contrasts of interest will be estimated and then combined across imputations using standard multiple imputation rules.

Additional scenarios for sensitivity analysis may be added and described in the RAP.

8.3.5.2. Safety Analyses

Subject demographics, medical history, prior and concomitant medications, study medication exposure, vital sign measurements, clinical laboratory values, 12-lead ECG readings, physical examination assessments, and AE rates will be summarized by treatment group using descriptive statistics. For continuous variables, these summaries will include sample size, mean, median, standard deviation, minimum, and maximum. For categorical variables, the summaries will include frequencies and corresponding percentages. Some graphical summaries may be provided as well. No inferential testing will be performed on the safety variables.

For selected AEs of special interest, such as hypoglycemia, the exposure-adjusted incidence rate will also be calculated as the number of events in a given period divided by the total person time on treatment of subjects at risk within the same period. The exposure-adjusted incidence rate will be expressed as an annualized rate (expected number of events per 100 person-years).

Adverse events will be coded using MedDRA. Adverse events will be summarized in various subsets, including treatment-emergent AEs, related AEs, AEs leading to treatment discontinuation or withdrawal from study, SAEs, fatal AEs, etc. Adverse events will also be summarized by maximum intensity (mild, moderate, and severe).

Treatment-emergent AEs will be defined as any AEs, regardless of relationship to the investigational product, that occur after the first dose of the randomized study medication. Treatment-emergent AEs will also be further defined as on-therapy or post-therapy AEs for summary purposes.

Treatment-related AEs will be defined as any AEs that are considered by the investigator to be possibly, probably, or definitely related to the investigational product. In addition, if relationship information is missing, the AE will be considered treatment related.

Adverse events of special interest will also be summarized.

The number and percentage of subjects reporting specific events, such as specific GI events and injection site reactions, at each study week will be summarized and plotted over time. Characteristics of specific events, such as time to first occurrence, occurrence relative to preceding dose, and duration, will be summarized.

Hypoglycemic events will be analyzed separately from other AEs. All hypoglycemic events will be classified as severe, documented symptomatic, asymptomatic, probable symptomatic, and pseudohypoglycemia, as defined in Section 6.3.1.

Incidence (in total and by each category) of hypoglycemia, daytime hypoglycemia, and nocturnal hypoglycemia will be determined. Daytime hypoglycemia is defined as hypoglycemic events with an onset between 06:00 hours and 00.00 hours (inclusive). Nocturnal hypoglycemia is defined as hypoglycemic events with an onset between 00:01 hour and 05:59 hours (inclusive). The incidence of hypoglycemia with blood glucose <56 mg/dL (<3.1 mmol/L), regardless of symptoms, will also be determined.

Estimated GFR will be calculated using the MDRD formula and summarized descriptively.

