Note: A fasting HbA_{1c} value may be determined using a Metrika kit (Metrika, Inc, Sunnyvale, California) or other finger-stick procedure to provide an initial guide of subject eligibility for investigators. The test is not required. The HbA_{1c} value obtained at this screening visit is to be used as a guide for the investigator. If the investigator feels that a subject is a good candidate for the study, the subject should continue with the screening visit and have HbA_{1c} assessed through the central laboratory. The central laboratory measure will serve as the official HbA_{1c} value to determine subject eligibility for entry into the Standardization Phase.

After Screening, subjects meeting all eligibility criteria will enter a 4-week Standardization Period to transition from their current basal-bolus regimen to insulin glargine plus insulin lispro. Subjects already on insulin glargine plus insulin lispro will also enter the Standardization Period. During the Standardization Period, the basal-bolus insulin regimen may be adjusted to achieve glycemic targets as close to normal as possible without untoward hypoglycemia in accordance with product labeling in the respective country and standard of care at the study center. Subjects will also receive training on the use of albiglutide injector pens and sterile techniques for self-administration in preparation for the Treatment Period, during which the investigational product (albiglutide) will be administered at home. See Section 5.1 for further details.

After the Standardization Period, subjects meeting additional criteria for randomization will be stratified by screening HbA_{1c} value (<8.0% versus $\geq 8.0\%$), age (<65 years versus ≥ 65 years), and current use of background metformin (metformin use versus no metformin use). Approximately 794 subjects will be randomly assigned to 1 of 2 treatment groups in a 1:1 ratio such that

- Approximately 397 subjects are randomly assigned to albiglutide + insulin glargine (with insulin lispro discontinuation at Week 4) (with or without metformin)
- Approximately 397 subjects are randomly assigned to intensification of insulin glargine + insulin lispro (with or without metformin)

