5.5. Treatment Compliance

Accountability will be done for the investigational product (albiglutide) and other study treatments (insulin glargine and insulin lispro) at the time points specified in the Time and Events Table ([Table 5](#)). Subjects will be instructed to return all unused investigational product and used injector pens in order to perform drug accountability and determine compliance.

Acceptable overall compliance for IP (albiglutide) and other study treatments (insulin glargine and insulin lispro) in this study will be $\geq 80\%$. Site personnel should confirm that subjects are taking their doses of albiglutide and insulin glargine and lispro insulin, if appropriate, as prescribed by their physician. Adherence will be monitored for the duration of the study.

Subjects will be instructed to take their metformin as prescribed by their physician and will continue on this dose for the duration of their participation in the study unless there is a decline in kidney function (Section [5.1.1](#) and [Table 2](#)). Adherence to dosing instructions for metformin will be monitored for the duration of the study.

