6.6. Treatment Compliance

Investigational product accountability will be done for albiglutide at each study visit after the baseline visit through the end-of-treatment visit (Visit 9, Week 26).

Albiglutide treatment compliance will be calculated as total number of doses administered divided by total number of doses expected based on the last dose date at the end of active treatment period. Total number of albiglutide administered during the treatment period will be computed as the number of expected dose minus the number of missed dose. For the number of expected dose, if subject completes the treatment, it will be 26. If subject doesn't complete the treatment, the number of expected dose will be equal to the number of weeks between treatment start date and treatment end date. The number of missed dose information, treatment start and end date are captured on the albiglutide administration CRF page. Treatment compliance will be summarized for all subjects, as well as for subjects who discontinue treatment early and subjects who complete active treatment. Summary statistics for treatment compliance percentages, as well as the number and percentage of subjects who are $<80\%$ and $\geq 80\%$ compliant will be reported for the Safety Population. Individual subject compliance information will also be listed.

Treatment compliance of subjects for insulin glargine and insulin lispro will be assessed by the investigator at each visit and reported on the eCRFs. At each visit on or after baseline, the investigator will answer "yes/no" to the question of "Do you believe the subject has been compliant with their insulin regimen at least 80% of the time". If the investigator answered "yes" for all the postbaseline visits for treatment compliance assessment (Week 4, 10, 18, and 26), the subject will be considered as being $\geq 80\%$ compliant to the treatment during the entire study period. For subjects who discontinued the study early, the same rule will apply and the assessment of overall compliance will be based on the data from the completed visits. The number and percentage of subjects in each compliance category will be summarized overall and by study visit for the safety population. Individual subject compliance information will be listed.

Acceptable overall compliance for IP (albiglutide) and other study treatments (insulin glargine and insulin lispro) in this study will be $\geq 80\%$.

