8.3.2.3. Treatment-Related Adverse Events

Treatment-related AEs will be defined as any AEs that are considered by the investigator to have a reasonable possibility to be related to the study treatment. If a relationship to the study treatment is missing or unknown after the start of treatment it will be assumed, for the purpose of analyses, to be treatment-related.

A summary of the number and percentage of subjects with treatment-related AEs will be displayed. The treatment-related AE data will be categorized and presented in a manner similar to that described above for the general AE summaries for both the on-therapy and post-therapy therapeutic phases.

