8.3.5.1. Hypoglycemic Events

Hypoglycemic events merit special attention in the development and study of drugs for the treatment of T2DM since they are often related to the efficacy of a compound. In order to accomplish this, hypoglycemic event data including supplemental hypoglycemic event information not collected on AE eCRF page are reported on a separate hypoglycemic event eCRF page. However, any hypoglycemic event that meets the criteria for a serious AE will also be included in the serious AE summaries.

Analysis of on-therapy hypoglycemic events will include all AEs coded to the preferred term of 'Hypoglycemia'. For on-therapy hypoglycemic events the number and percentage of subjects with events, the number of events, the incidence rate (per 100 person-years) and AE density (per 100 person-years) by the severity of the event defined by American Diabetes Association [ADA], SAE status, relationship to the investigational product, and withdrawal status will be summarized by treatment group. The events will also be summarized according to intervention provided, action taken with regard to background and anti-hyperglycemic medications and onset week and glucose levels. All hypoglycemic events will be classified as severe, documented symptomatic,

asymptomatic, probable symptomatic, or pseudohypoglycemia per the American Diabetes Association criteria) criteria.

The number of events of hypoglycemia with confirmed home blood glucose monitoring < 3.9 mmol/L and/or requiring third party intervention (i.e., severe, documented symptomatic and asymptomatic hypoglycemic events) in 3 monthly intervals (i.e., from Baseline to Week 12, >Week 12 to Week 26) will be summarized by treatment group. The exposure-adjusted event rate will be compared between treatment groups using a Poisson regression model with offset for the person-year, which will include HbA_{1c} stratum, age (<65 years versus ≥65 years), current use of metformin (metformin use versus no metformin use), and region as covariates.

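### The hypoglycemia relatedness summary is tied to the investigational product, which means albiglutide, so read as written it is not comparable between arms and conflicts with its own table title

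*Protocol*

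**What the plan says.** Protocol 8.3.5.2 counts an adverse event as treatment-related if it is "considered by the investigator to be possibly, probably, or definitely related to the investigational product", and adds that "if relationship information is missing, the AE will be considered treatment related".

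Both documents say what the investigational product is. Protocol 3.1 refers to the Treatment Period, "during which the investigational product (albiglutide) will be administered at home". Protocol 5.5 states: "Accountability will be done for the investigational product (albiglutide) and other study treatments (insulin glargine and insulin lispro"). SAP 6.6 draws the same line: "Acceptable overall compliance for IP (albiglutide) and other study treatments (insulin glargine and insulin lispro) in this study".

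The SAP changes the general definition. Under SAP 8.3.2.3 a related event is one judged "to have a reasonable possibility to be related to the study treatment", and a missing or unknown relationship after the start of treatment is again counted as related. Table 3.21 reports events by relation to each individual study treatment.

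For hypoglycemia, SAP 8.3.5.1 keeps the narrower term: "relationship to the investigational product, and withdrawal status will be summarized by treatment group". The title of the matching display, Table 3.71, names study medication instead. SAP 2.1, which records departures from the protocol's analysis, has one entry, on prescribed insulin dose.

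**The concern.** Relatedness to albiglutide alone cannot work as a between-arm summary when one arm never receives albiglutide. Hypoglycemia is where this matters most. The protocol's risk table calls it the most common adverse effect of insulin, and a difference in its frequency is a key secondary objective. A reader of the study report would take the related-hypoglycemia rows as describing both regimens. Under the wording of SAP 8.3.5.1 they would describe only what investigators attributed to albiglutide, plus any events with no relationship recorded.

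There is also a practical problem. The text and the table title give a programmer two different instructions for the same rows, and nothing in the SAP says which governs.

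**Working it through.** No sample size, power or event count enters this point, so there is no figure to reproduce. The check is a comparison of definitions.

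**1. Who takes albiglutide.** Protocol Table 2 gives albiglutide only to the albiglutide group and lists none for the lispro group. Both groups take insulin glargine. The albiglutide group also takes lispro at half dose until Week 4, and again if it is re-introduced after Week 8.

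**2. What each rule counts as related.**

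| Arm | Investigator's attribution | SAP 8.3.5.1 text (albiglutide) | SAP 8.3.2.3 (study treatment) |
|---|---|---|---|
| Lispro | Glargine or lispro | Not related | Related |
| Albiglutide | Albiglutide, with or without insulin | Related | Related |
| Albiglutide | Insulin only | Not related | Related |
| Either | No study treatment | Not related | Not related |
| Either | Missing | Related, if the missing-data rule carries over | Related |

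The rules differ in the second and fourth lines of the table as read from its heading: events attributed to insulin in the lispro arm and events attributed only to insulin in the albiglutide arm. The first loss is complete for assessed events; the second is partial. That difference makes the rows non-comparable.

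**3. Whether the corrected general definition reaches hypoglycemia.** Mostly it does not. SAP 8.3.2 leaves hypoglycemic events out of the adverse event summaries unless otherwise specified; the exceptions it names are serious events, events leading to withdrawal from treatment, and pre-therapy events. Non-serious on-therapy hypoglycemia is therefore generally outside the related-event tables, and SAP 8.3.5.1 with Table 3.71 is its dedicated relatedness summary.

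**4. Whether two counts could appear in one report.** Yes. SAP 8.3.2.1 and 8.3.2.5 put hypoglycemia into the register-format summaries. These appear to be Tables 3.17 and 3.20, whose titles include relation to treatment. If Table 3.71 follows the 8.3.5.1 text, its related count could differ from theirs for the same events.

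**5. What does not depend on relatedness.** The key secondary endpoint (SAP 8.1.2.2) is the percentage of subjects with severe or documented symptomatic hypoglycemia, tested by CMH with supportive logistic regression. The Poisson comparison in SAP 8.3.5.1 and the incidence summaries by category, time of day and glucose below 56 mg/dL also count events whatever their attribution.

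**The case against.** The best defense is that the term is loose drafting rather than a rule. Protocol 5.2 has sites trigger shipment of investigational product at each randomization, and protocol 6.3.6 withdraws it from any subject who meets liver stopping criteria, so in places it seems to cover both arms. The heading of SAP 8.3.4 uses investigational product while its text speaks of randomized study drug by treatment group. Protocol 8.3.5.2 also uses the term when defining treatment-emergent events, and SAP 8.3.2.2 rewrites that sentence to cover albiglutide or the other study treatments. Protocol 8.3.5.2 says hypoglycemia is analyzed separately and lists no relatedness analysis for it, so the issue comes down to one SAP phrase that its own table title contradicts.

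Much of this stands. The intent was probably a definition covering both arms, and the table title supports that: exclusion criterion 17 in protocol 4.3 counts the two insulins among the potential study medications. But where the documents say what the term means, they say albiglutide. The SAP authors replaced it in 8.3.2.2 and 8.3.2.3 and left it in 8.3.5.1. A programmer should not have to infer intent from a title.

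**Conclusion.** SAP 8.3.5.1 is wrong as written and conflicts with the title of Table 3.71. If the table follows the text, no lispro-arm hypoglycemic event is related by investigator assessment, and insulin-only attributions disappear from the albiglutide arm. The effect is confined to one descriptive breakdown; no test, type I error or efficacy conclusion changes. The documents give no expected rate of insulin-attributed hypoglycemia, so no percentage can be put on the distortion.

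This rests on two assumptions: that investigational product carries the meaning stated in protocol 3.1 and 5.5 and SAP 6.6, and that the table is built from the text rather than from its title.

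Three stronger readings are not supported:

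- A reader might infer that the lispro arm cannot have any related event, or must show zero among its roughly 397 subjects. The missing-relationship rule in protocol 8.3.5.2 applies to either arm, and SAP 8.3.2.3 lets lispro-arm events be related in the general tables.
- A reader might infer that all related-event tables are biased. SAP 8.3.2.3 and Table 3.21 already work from study treatment.
- A reader might infer that the trial's hypoglycemia comparison is reversed. The endpoint and rate analyses count every qualifying event regardless of attribution.

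**What to change.** In SAP 8.3.5.1 and protocol 8.3.5.2, define related as related to any study treatment in the subject's regimen: albiglutide, insulin glargine or insulin lispro. This agrees with SAP 8.3.2.3 and the title of Table 3.71. State that the missing-relationship rule applies to hypoglycemic events too.

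In Table 3.71, show the split by component where the hypoglycemia eCRF captures it. Table 3.21 shows that this split is planned for adverse events, but hypoglycemia has its own eCRF page, so confirm the capture first.

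Add an entry to SAP 2.1 for the changed related-event definition. It should cover both the move from investigational product to study treatment and the move from the three-level wording (possibly, probably, definitely) to a reasonable possibility.

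The cost is wording in two sections and one added entry. No new data or analysis is needed if the eCRF records relation to each treatment; if it does not, the component split has to be left out and the limitation stated.
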